5.1.1.1.5 Definition of Baseline values

A Baseline value for clinical variables is defined as the latest measurement on or prior to the first dosing day of study medication, regardless of the time of the measurement, for the Treatment Period. If a Baseline assessment is taken on the same day as first administration of study medication, it is eligible to be used as the Baseline value, even in the case that the time of the assessment is recorded as taking place after the time of first study medication administration. One exception to this rule is plasma concentration. If Baseline plasma concentration is measured at a time after the first administration of study medication, then it will not be eligible to be considered as a Baseline plasma concentration. Such cases will be discussed with the quantitative clinical pharmacologist.

If a Baseline measurement is missing or not collected, and a Screening value is available, the Screening value will be utilized as Baseline instead. If no measurement is available prior to receiving study medication, then the Baseline value is treated as missing.

Baseline values for component scores should be computed using components from the same visit where the relevant measurements were recorded prior to dosing. For example, if the Screening visit has all of the components, but the Baseline visit is missing one or more components, the Baseline value for the component score should be calculated using the Screening visit values.

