An additional sensitivity analysis will be performed on DLQI 0/1 at Week 16 which will exclude study participants with a missing Baseline DLQI score. Missing baseline DLQI scores can be due to study participants not completing an assessment until after the first dosing visit or due to late entry of the intended Baseline scores. The scores should be entered directly into the database by the study participant at the Baseline visit, however due to some technical problems for a few subjects this was not possible, and the scores were collected on paper and entered at a later date.

orization

As only the date that the scores were entered electronically is captured in the database, these records are considered post-baseline for the purpose of analysis.

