5.4.1.4 Supplementary analyses

No supplementary analysis will be conducted.

Tertiary/Exploratory Endpoint(s) Analysis 5.5

The tertiary efficacy variables will be analyzed for all study participants in the RS.

5.5.1 **Binary endpoints**

Binary (responder) variables as listed below will be summarized using frequency tables by treatment group for each visit. Missing data that are not preceded by an intercurrent event, as well as any data following an intercurrent event will be imputed as non-response. While this any nations approach is described as a composite strategy for intercurrent event handling, it is equivalent to applying non-responder imputation (NRI). Observed case results will also be displayed:

- PASI75/90/100 response over time
- IGA 0/1 & IGA 0 response over time •
- PSD (P-SIM) response for each item over time •
- Scalp IGA 0/1 response over time •
- Percentage of study participants with absolute PASI score $\leq 1, \leq 2, \leq 3$, and ≤ 5 over time
- Percentage of study participants with absolute BSA affected by PSO=0%, $\leq 1\%$, $\leq 3\%$ and <5% over time
- DLQI 0/1 response over time

The following endpoints will be derived using observed data only (no imputation): PSD (P-SIM) Itch, Pain and Scaling Compliance rate at Baseline and Week 16 PSD (P-SIM) Itch, Pain and Scaling Completion rate at Baseline and Week 16

Figures displaying the response over time using NRI data will be produced for PASI, IGA, Scalp IGA and DLQI 0/1 response variables.

Continuous endpoints 5.5.2

Continuous variables will be summarized using descriptive statistics by treatment group for each visit. No imputation will be applied to continuous variables, only observed data will be summarized:

Absolute and percent change from Baseline in PASI score over time

- Absolute and percentage change in BSA affected by PSO over time
- Change from Baseline in DLQI Total Score over time
- Absolute and percent change from Baseline in PSD (P-SIM) scores for each item over time

Figures displaying the results over time will be produced for mean percent improvement from baseline in PASI score and mean percent change from baseline in BSA respectively.

Bimekizumab

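### DLQI scores meant as Baseline but taken on paper are dated by electronic entry, which leaves a few participants without a Baseline DLQI

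*SAP*

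**What the plan says.** **The DLQI rule.** SAP 5.4.1.3 adds a sensitivity analysis of DLQI 0/1 at Week 16 "which will exclude study participants with a missing Baseline DLQI score". It names two causes of a missing Baseline score. One is "study participants not completing an assessment until after the first dosing visit". The other is late entry. Participants were meant to key in their own answers when they came for Baseline, but the SAP notes: "however due to some technical problems for a few subjects this was not possible". What happened instead in those cases, by its account, is that "the scores were collected on paper and entered at a later date". The SAP then gives its reason for the classification: "As only the date that the scores were entered electronically is captured in the database". The consequence it draws is that such "records are considered post-baseline for the purpose of analysis".

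**The general Baseline rule.** Under SAP 5.1.1.1.5, Baseline is the last measurement made no later than the day of first dosing, "regardless of the time of the measurement". The sentence after it shows that this phrase concerns clock time on the dosing day: a same-day assessment still counts if its recorded time is after the injection. A Screening value may stand in for a missing Baseline. Without any pre-dose value, Baseline is missing.

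**The schedule.** Protocol Table 1-1 has DLQI at Baseline and Weeks 2, 4, 8, 12 and 16, and none at Screening.

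**Where Baseline DLQI is used.** SAP 5.5.2 lists "Change from Baseline in DLQI Total Score over time" among the tertiary summaries, on observed data without imputation. SAP 6.1.1.2 lists the DLQI total score as a Baseline characteristic, both as a score and split at zero.

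**Where it is not used.** DLQI 0/1 at Week 16 is an absolute score (Protocol 9.3.3; SAP 5.4.1.1.6), analyzed on the Randomized Set with a nominal p-value only (SAP 5.4).

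**The concern.** The date on which a score was typed into a database is not the date on which the participant answered the questionnaire. SAP 5.1.1.1.5 turns on the second date, while SAP 5.4.1.3 uses the first because it is the only one stored. A score that may well have been given before the first injection is then treated as if it came after it.

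Two things are at stake. The change-from-Baseline and Baseline summaries lose participants for a reason unrelated to their disease or treatment. The added sensitivity analysis also becomes hard to read: it removes participants with a late keystroke along with participants who really had no pre-dose assessment. If its result differs from the main analysis, the reader cannot tell which group caused the difference.

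**Working it through.** The plan gives no figure on this point. The sample-size calculation rests on PASI90 and does not involve DLQI. The check is therefore a trace of the rule through the plan, followed by counting.

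**Step 1: does the paper record have a Baseline value?**
- SAP 5.1.1.1.5 asks when the measurement was made.
- SAP 5.4.1.3 answers with the entry date, which is later, so the record is post-baseline.
- The Screening fallback needs a Screening DLQI, and Protocol Table 1-1 has none.
- Result: Baseline DLQI is missing for every affected participant.

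**Step 2: which analyses lose these participants?**

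| Analysis | Needs Baseline DLQI? | Effect |
|---|---|---|
| DLQI 0/1 at Week 16, main analysis (SAP 5.4.1.2.1) | No | 0 lost |
| DLQI 0/1, observed cases (SAP 5.4.1.3) | No | 0 lost through this rule |
| DLQI 0/1, additional sensitivity analysis (SAP 5.4.1.3) | Yes, by its exclusion rule | All affected participants lost |
| Change from Baseline in DLQI (SAP 5.5.2) | Yes, no imputation | All lost, at every visit |
| Baseline DLQI summary (SAP 6.1.1.2) | Yes | Score absent |

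**Step 3: how many?** The SAP states neither the count nor the arm. Assume k = 1 to 5 of the 45 planned, with nobody else lacking a Baseline score. The share is k/45:
- k = 1: 1/45 = 2.2%, leaving 44
- k = 3: 3/45 = 6.7%, leaving 42
- k = 5: 5/45 = 11.1%, leaving 40

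One participant is 1/30 = 3.3% of the bimekizumab arm or 1/15 = 6.7% of the placebo arm.

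**Step 4: how far could the sensitivity estimate move?** The documents give no DLQI response rates. As an illustration only, assume 18/30 responders on bimekizumab and 2/15 on placebo, a risk difference of 60.0% − 13.3% = 46.7 points. The extremes over every choice of arm and response status are:

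| Excluded | Lowest difference | Highest difference |
|---|---|---|
| 1 | 17/29 − 2/15 = 45.3 | 18/30 − 1/14 = 52.9 |
| 3 | 15/27 − 2/15 = 42.2 | 18/29 − 0/13 = 62.1 |
| 5 | 13/25 − 2/15 = 38.7 | 18/27 − 0/13 = 66.7 |

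These are worst cases, not expectations. They show that in arms of 30 and 15 a handful of exclusions can visibly shift the comparison, so it matters whether the right people are excluded.

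**The case against.** The strongest reply is that the SAP cannot treat as pre-dose a record that its database does not show to be pre-dose. With only an entry date stored, classing the score as post-baseline is a cautious choice. It is disclosed with its reason and was added openly in SAP Amendment 1. Leaving out participants without a verifiable Baseline is the declared purpose of the extra analysis, and a wider exclusion makes for a stricter robustness check. This stands as a defence of the choice given the stored data. It does not explain why the stored data should be the last word when paper forms exist, nor why two different causes are pooled.

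A reader might go further than the documents allow in several ways:

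- **That valid Baseline data are discarded.** SAP 5.1 provides for listings of all documented data, so the records are kept and reclassified. That they were completed before dosing is a plausible inference, but the SAP does not say that the forms carry a completion date.
- **That participants are wrongly excluded.** They meet the exclusion rule as the SAP defines it. The weakness lies in how Baseline status is assigned.
- **That the time-of-measurement wording in SAP 5.1.1.1.5 already admits these scores.** It covers clock time on the dosing day, not a record whose only date is later.
- **That the DLQI secondary endpoint is compromised.** It uses no Baseline score, keeps every randomized participant and carries no formal test.
- **That pre-dose scores will appear as on-treatment values in by-visit tables.** The SAP does not say how these records are assigned to visits, so this is an open question and not a finding.

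**Conclusion.** The point holds as a minor inconsistency with limited reach. The entry-date rule in SAP 5.4.1.3 does not fit the measurement-date rule in SAP 5.1.1.1.5. It leaves the affected participants with no Baseline DLQI, and so outside the tertiary change from Baseline, the Baseline DLQI summary and the additional sensitivity analysis. That sensitivity analysis also mixes late entry with truly late assessment.

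The size is unknown. The range of 2.2% to 11.1% rests on reading the SAP's vague count as 1 to 5 of 45. The main DLQI 0/1 analysis changes by no participants, and no formal inference is touched. Whether the scores can be restored as Baseline depends on whether the paper forms show a completion date, which the documents leave open.

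**What to change.** 1. Check the paper forms. Protocol 10.1.7 counts completed scales and quality-of-life questionnaires among source documents, and 10.1.6 requires source data to be kept and monitored. Where the form verifies completion on or before the first dosing day, use the score as Baseline in all DLQI summaries.
2. Limit the exclusion in the additional sensitivity analysis to participants whose score was completed later or cannot be verified.
3. Report the number with a missing Baseline DLQI by arm and by cause, keeping late entry apart from late assessment.
4. Where no date can be verified, repeat the analysis with the paper scores accepted as Baseline, so that the reader sees both versions.

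The cost is a small source-data check for a few participants, a short clarification in SAP 5.4.1.3 and at most one extra table. The downside is that step 1 works only if the forms carry a date. If they do not, steps 3 and 4 still make the analysis interpretable.

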5.4.1.4 Supplementary analyses

No supplementary analysis will be conducted.

Tertiary/Exploratory Endpoint(s) Analysis 5.5

The tertiary efficacy variables will be analyzed for all study participants in the RS.

5.5.1 **Binary endpoints**

Binary (responder) variables as listed below will be summarized using frequency tables by treatment group for each visit. Missing data that are not preceded by an intercurrent event, as well as any data following an intercurrent event will be imputed as non-response. While this any nations approach is described as a composite strategy for intercurrent event handling, it is equivalent to applying non-responder imputation (NRI). Observed case results will also be displayed:

- PASI75/90/100 response over time
- IGA 0/1 & IGA 0 response over time •
- PSD (P-SIM) response for each item over time •
- Scalp IGA 0/1 response over time •
- Percentage of study participants with absolute PASI score $\leq 1, \leq 2, \leq 3$, and ≤ 5 over time
- Percentage of study participants with absolute BSA affected by PSO=0%, $\leq 1\%$, $\leq 3\%$ and <5% over time
- DLQI 0/1 response over time

The following endpoints will be derived using observed data only (no imputation): PSD (P-SIM) Itch, Pain and Scaling Compliance rate at Baseline and Week 16 PSD (P-SIM) Itch, Pain and Scaling Completion rate at Baseline and Week 16

Figures displaying the response over time using NRI data will be produced for PASI, IGA, Scalp IGA and DLQI 0/1 response variables.

Continuous endpoints 5.5.2

Continuous variables will be summarized using descriptive statistics by treatment group for each visit. No imputation will be applied to continuous variables, only observed data will be summarized:

Absolute and percent change from Baseline in PASI score over time

- Absolute and percentage change in BSA affected by PSO over time
- Change from Baseline in DLQI Total Score over time
- Absolute and percent change from Baseline in PSD (P-SIM) scores for each item over time

Figures displaying the results over time will be produced for mean percent improvement from baseline in PASI score and mean percent change from baseline in BSA respectively.

Bimekizumab

In addition, the entire distribution of data for PSD response based on each of the items will be evaluated via continuous plots showing the absolute change from Baseline on the X-axis and the percent of study participants experiencing that change on the Y-axis. This distribution curve will reveal the extent to which overall results are driven by outliers who improve or worsen more than others. The cumulative distribution function (CDF) is the probability that the variable takes a value less than or equal to x. That is:

 $x \mapsto Fx(x) = P(X \le x)$ where the right-hand side represents the probability that the random variable X takes on a value less than or equal to x. The probability that X lies in the interval [a, b] is therefore:

Fx(b) - Fx(a) if a < b

Cumulative distribution plots will be provided for absolute change from Baseline in PSD scores at Week 16 for each PSD item.

5.5.3 Time to PASI50/70/90/100 response

Time to PASI50, PASI75, PASI90, and PASI100 response (in days) during the Treatment Period will each be calculated as:

Date of first PASI xx response – Date of first study drug administration + 1.

with xx representing 50, 70, 90, 100 respectively. All visits including unscheduled visit are considered.

Time to PASI50, PASI75, PASI90, and PASI100 response will be estimated using the Kaplan-Meier product-limit method for each treatment group. Study participants who discontinue IMP prior to achieving a response will be censored at the date of the last observed PASI assessment on or prior to the date of IMP discontinuation. Study participants who complete the study without achieving the given response will be censored at the date of the last observed PASI assessment in the Treatment Period. Study participants will be censored at Baseline (Day 0) if there is no Baseline PASI assessment or no post-Baseline PASI assessment in the Treatment Period.

Kaplan-Meier plots of time to PASI responses will also be provided by treatment group. In these Kaplan-Meier plots, the line will start at 0 (since there are no responders at Week 0) and will increase over time, representing time to achieving the response.

The median time to response, including the 2-sided 95% CI, will be calculated for each treatment group.

Safety Analyses

Safety variables will be analyzed for all study participants in the SS.

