1.3 Schedule of activities

Table 1-1: Schedule of study assessments

Protocol activity	Visit ^a / Week	Treatment Period							SFU ^c
		Screening ^b	Baseline (W0)	W1	W2	W4	W8	W12	
Informed consent	X								
Inclusion/exclusion	X	X							
Urine drug screen	X								
Demographic data	X								
PSO history	X								
Significant past medical history and concomitant diseases	X	X ^d							
Physical examination ^{e, f}	X	X					X	X	X
Height		X							
Body weight		X						X	
Vital signs ^g	X	X	X	X	X	X	X	X	X
Hematology and biochemistry	X	X	X	X	X		X	X	X
Urinalysis	X	X						X	X
ECG	X							X	
Pregnancy testing ^h	X	X			X	X	X	X	X
Hepatitis B and C testing ⁱ	X								
HIV testing ^j	X								
Chest x-ray ^k	X								

Table 1-1: Schedule of study assessments

Protocol activity	Visit ^a / Week	Treatment Period							SFU ^c	
		Screening ^b	Baseline (W0)	W1	W2	W4	W8	W12		W16/ PEOT
IGRA TB test		X								
TB questionnaire ^l		X	X					X ^l		X
PASI		X	X	X	X	X	X	X	X	X
IGA		X	X	X	X	X	X	X	X	X
Scalp IGA ^m			X		X	X	X	X	X	X
Percentage of BSA		X	X	X	X	X	X	X	X	X
DLQI			X		X	X	X	X	X	
PHQ-9		X	X			X	X	X	X	X
C-SSRS		X	X			X	X	X	X	X
PSD (P-SIM) (daily)		X	X	X	X	X	X	X	X	
Concomitant medication		X	X	X	X	X	X	X	X	X
AEs		X	X	X	X	X	X	X	X	X
IRT ^{n, o}		X	X	X	X	X	X	X	X	X
Blood sample for PK plasma BKZ concentrations and anti-BKZ antibodies ^p			X			X	X	X	X	X
BKZ or placebo administration ^{n, o}			X			X	X	X		

AEs=adverse events; BKZ=bimekizumab; BSA=body surface area; DLQI=Dermatology Life Quality Index; ECG=electrocardiogram; eCRF=electronic Case Report Form; C-SSRS=Columbia Suicide Severity Rating Scale; HBcAb+=positive for anti-hepatitis B core antibody; HBsAg+=positive for hepatitis B surface antigen; HCV=hepatitis C virus; HIV=human immunodeficiency virus; IGA=Investigator’s Global Assessment; IGRA=interferon-gamma release assay; IMP=investigational medicinal product; IRT=interactive response technology; MAP=Managed Access Program; PASI=Psoriasis Area Severity Index; PEOT=Premature End of Treatment; PHQ-9=Patient Health Questionnaire-9; PK=pharmacokinetic; PSD=patient symptom diary; P-SIM=Patient Symptom and Impact Measure; PSO=psoriasis; SFU=Safety Follow-Up; TB=tuberculosis; W=Week

- ^a Visit windows of ± 3 days from the first dose (W0) to the Week 16 visit. The SFU Visit window is ± 7 days from last dose.

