9.3.4 Tertiary efficacy endpoint analyses

The tertiary efficacy variables will be analyzed for all study participants in the RS.

Binary (responder) variables will be summarized using frequency tables by treatment group for each visit; nonresponder imputation (NRI) and observed case results will be displayed.

Continuous variables will be summarized using descriptive statistics by treatment group for each visit. No imputation will be applied to continuous variables, only observed data will be summarized.

Time to PASI50, PASI75, PASI90, and PASI100 response will be estimated using the Kaplan-Meier product-limit method for each treatment group. Time to a given response will be defined as the length in days from the first dose of IMP until the first date when the response is achieved. Study participants who discontinue IMP prior to achieving a response will be censored at the date of the last observed PASI assessment on or prior to the date of IMP discontinuation. Study participants who complete the study without achieving the given response will be censored at the date of the last observed PASI assessment.

Study participants will be censored at Baseline (Day 0) if there is no Baseline PASI assessment or no post-Baseline PASI assessment.

The median time to response, including the 2-sided 95% CI, will be calculated for each treatment group.

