Derived variables in general will display the mean, SD and median to 1 more decimal place than the variables used in the derivation. If the number of decimal places reported in the raw data is varied then use either the maximum raw number of reported decimal places or 3, whichever is the lowest, as a guide for the descriptive statistics.

Statistical tests of efficacy variables will be presented as two-sided p-values rounded to three decimal places. P-values less than 0.001 will be presented as "<0.001" and p-values greater than 0.999 will be presented as ">0.999."

Per protocol, visit windows of ± 3 days from the first dose (W0) to the Week 16 visit are permissible; for SFU Visit, permissible window is ± 7 days from last dose + 20 weeks. For byvisit presentations, data from unscheduled visits should generally not be included. If the data of unscheduled visit is the only record prior to first IMP administration, it will be an exception and treated as baseline value. In case of repeated laboratory tests at a particular visit, the last measurement should generally be used for visit presentation in by-visit summaries.

In cases where vendor data is assigned to an unscheduled visit instead of a scheduled visit, the assessments will be mapped into the scheduled visit if the assessment dates fall into the permissible window, as detailed above.

A complete set of data listings containing all documented data and all calculated data (eg, change from Baseline) will be generated.

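### Censoring Week 16 nonresponders on their own visit date over-weights first responses seen at Week 16, so the time-to-PASI-response curves can end above the observed response (minor; tertiary endpoint)

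*SAP*

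**What the plan says.** SAP 5.5.3 defines the event time as "Date of first PASI xx response – Date of first study drug administration + 1", and adds that "All visits including unscheduled visit are considered". Times are thus calendar days, not nominal weeks. Participants who finish "without achieving the given response will be censored at the date of the last observed PASI assessment" in the Treatment Period. Protocol 9.3.4 has the same rule: time is "the length in days from the first dose of IMP until the first date when the response is achieved", and "Study participants who complete the study without achieving the given response will be censored at the date of the last observed PASI assessment".

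Table 1-1 of the protocol (footnote a) allows "Visit windows of ± 3 days from the first dose (W0) to the Week 16 visit", and SAP 5.1 repeats this. Nothing in SAP 5.5.3 maps Week 16 dates to a nominal day or sets a common censoring time.

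The planned outputs are Kaplan-Meier plots and the median time with its 95% CI, by arm. The endpoint is tertiary and no test is attached to it.

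**The concern.** A PASI response can be seen only at a visit. By Week 16, a participant seen on Day 110 without response has already had the final chance to respond, just like one seen on Day 116. Kaplan-Meier does not know this. It treats the Day 110 nonresponder as someone whose outcome after Day 110 is unknown, and spreads that person's weight over those still to be seen. A responder seen on Day 115 is then divided by a risk set from which known nonresponders have been removed. Censoring here is decided by the assessment itself, so it is not independent of the outcome.

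The error acts only upward and needs no dropout. It concerns people who complete the study, so it is separate from how early discontinuers are censored. At stake is the right-hand end of the plotted curves. With 15 placebo participants there is also some chance of a placebo median produced by visit scheduling alone.

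**Working it through.** **Inputs.** From the documents: 15 placebo and 30 bimekizumab participants, with planning counts of 2 and 21 PASI90 responders (2/15 = 13.3%, 21/30 = 70%; protocol 9.8, SAP 3). Window ±3 days. Week 16 is 112 days after first dose, which is Day 113 on the + 1 count, so the window is Days 110 to 116.

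Assumed, because the documents do not give them: which visit shows the first response, and how Week 16 dates scatter. Both are varied below. No dropout is assumed throughout, so the correct end of the curve is the observed proportion.

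**The plan's own figure.** The documents state no Kaplan-Meier figure. The one computed figure that uses 13.3% is the power. The continuity-corrected formula at 30 and 15 gives 95.6%, against 95% stated. It does not depend on SAP 5.5.3.

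**A case by hand.** Fifteen placebo participants; one responds before Week 16, leaving 14. Two are seen on each of Days 110 to 116, and one of the 14 is a first responder. With R still at risk on that person's day, the curve ends at 1 − (14/15)(1 − 1/R).

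| Responder's day | R | End of curve |
|---|---|---|
| 110 | 14 | 13.3% |
| 113 | 8 | 18.3% |
| 115 | 4 | 30.0% |
| 116 | 2 | 53.3% |

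The data are the same in each row, 2 responders of 15. Only the responder's visit date differs.

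**Average over random dates, one first response at Week 16.** With M at risk entering the window and dates uniform over 7 days, the mean of 1/R is (1/7) Σ [1 − (1 − k/7)^M] / (Mk/7), for k = 1 to 7.
- Placebo, M = 14: mean 1/R = 0.177, so the curve ends on average at 1 − (14/15)(0.823) = 23.2%.
- Bimekizumab, 20 earlier responders, M = 10: mean 1/R = 0.236, so 1 − (10/30)(0.764) = 74.5%.

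**Large samples, all first responses at Week 16.** 1 − Π(1 − p/k), k = 1 to 7, with p = 2/15: 1 − 0.981 × 0.978 × 0.973 × 0.967 × 0.956 × 0.933 × 0.867 = 30.2%.

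**Simulation** (uniform dates, events before censorings at ties, 20,000 runs):

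| Arm | First responses at Week 16 | Observed | Mean | Median | Curve ≥50% | Curve reaches 100% |
|---|---|---|---|---|---|---|
| Placebo, 2/15 | 0 | 13.3% | 13.3% | 13.3% | 0% | 0% |
| Placebo, 2/15 | 1 | 13.3% | 23% | 17% | 7% | 2% |
| Placebo, 2/15 | 2 | 13.3% | 31% | 25% | about 15% | 4% |
| Bimekizumab, 21/30 | 0 | 70% | 70% | 70% | – | 0% |
| Bimekizumab, 21/30 | 1 | 70% | 74.5% | 72% | – | 4% |
| Bimekizumab, 21/30 | 3 | 70% | 80% | 78% | – | 11% |

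**Sensitivity to the assumptions.** If each placebo responder has a 1/6, 1/3 or 1/2 chance of first responding at Week 16, the means are 16.5%, 19.6% and 22.9% (medians 13.3%, 13.3% and 16.1%). With both at Week 16, a triangular scatter gives mean 31.9% and median 23.6%; with 60% of visits on the target day, mean 29.0% and median 16.7%.

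**After the change.** With all Week 16 nonresponders censored at Day 116, every run ends at exactly 13.3% and 70%.

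**The case against.** The strongest reply is that this is a descriptive tertiary output and that the damage is easily overstated. Much of that stands.

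- **All curves inflated.** A reader might infer that the visit window distorts every curve throughout. It does not. Completers are censored only at Week 16, so scatter at earlier visits does no harm, and a curve with no first response at Week 16 is exact.
- **13.3% doubles.** A reader might infer a general doubling. That needs both placebo responders to respond first at Week 16, although PASI is also scored at Weeks 1, 2, 4, 8 and 12, and it is the mean of a skewed distribution. The documents give neither the timing of placebo responses nor the spread of visit dates. They describe response on bimekizumab as rapid (protocol 4.3), which suggests few first responses there at Week 16.
- **Mismatch with the Week 16 response rate.** This is the wrong yardstick. The curve counts anyone who ever responded, while the Week 16 rate counts response at that visit with nonresponder imputation. The two may differ anyway. The right comparison is the observed proportion who ever responded.
- **Planned numbers.** SAP 5.5.3 reports medians, not a Week 16 estimate, and a median reached before Week 16 is unchanged. By-visit response with nonresponder imputation is also planned (SAP 5.5.1) and is free of the problem.
- **Day 0 for Baseline censoring against + 1 for events.** This is cosmetic. Someone censored at Day 0 is in no risk set at an event.

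The reply does not remove the fault. When anyone does first respond at Week 16, the rule as written can give a wrong end to a planned curve, and nothing in the plan would tell a reader why.

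**Conclusion.** The point holds in a limited form. Under the stated rule, first responses at the Week 16 visit are over-weighted and the end of the curve can exceed the observed cumulative response. For placebo PASI90 at the planning counts, the average estimate runs from 13.3% (no excess) to about 31%. At that upper end, about one run in seven crosses 50% and would report a spurious placebo median. For bimekizumab at 21 of 30, one to three first responses at Week 16 move the average from 70% to between 74.5% and 80%.

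These sizes rest on no dropout, on the assumed visit of first response and on the assumed scatter of dates. The direction does not rest on those assumptions about timing and scatter. The co-primary analyses and the sample size are untouched. Severity: minor.

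**What to change.** In SAP 5.5.3, keep actual dates for events. Censor every participant who has a Week 16 PASI and no response at one common time at or after the end of the window: Day 116 on the + 1 count (112 + 3 + 1), or the latest Week 16 visit if later. Because protocol 9.3.4 carries the present rule, list the change in SAP 6.2. With no earlier dropout, the curve then ends at the observed cumulative response.

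Using nominal visit days for all events and censorings, with events first at ties, also removes the bias. It is not the same analysis, since event times and medians will differ, so the SAP should name one of the two.

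The cost is a sentence in SAP 5.5.3, an entry in SAP 6.2 and a small programming change. The one drawback is that the final censoring mark falls a few days after some visits.
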